Study Title: A Prospective Clinical Evaluation of the Bridging Technique Using AILEENE Vol. 2 Dermal Filler for the Treatment of Nasolabial Folds

IRAS Short Title: Bridging Technique Validation for Nasolabial Folds – JN-BRIDGE1

IRAS Project ID: 360828

REC Reference: 25/NW/0251

NHS REC Form Reference: 25/PR/1094

Sponsor Reference: JNL-BridgingNL-2025

Protocol Number: JN-BRIDGE-2025-01

Sponsor: JNL Aesthetics Limited, [name]

Chief Investigator: [name] [name] ([name] | MBBS | QCCP-qualified in Dermal Fillers & Neurotoxins)

NCT Number: (to be assigned upon PRS registration)

Document Title: Study Protocol

Version / Date: Version 1.0, 01 August 2025 – REC approved

Research Protocol

IRAS Project ID: 360828

Internal study reference code: JNL-BridgingNL-2025

Title: A Prospective Clinical Evaluation of the Bridging Technique Using AILEENE Vol. 2 Dermal Filler for the Treatment of Nasolabial Folds

Chief Investigator: [name] [name]

Sponsor: JNL Aesthetics Limited

Site: Ascencia Aesthetics Academy, [name]

Version: 1.0

Date: 01 August 2025

1. Background and Rationale

Nasolabial folds (NLFs), the lines extending from the sides of the nose to the corners of the mouth, are among the most common age-related concerns in aesthetic medicine. Loss of volume in deep facial fat compartments and changes in skin elasticity contribute to their formation. While several filler techniques are available and widely used, clinical practice lacks standardisation on a technique that balances safety, minimal invasiveness, and natural outcomes.

The Bridging Technique is a novel filler method that uses a blunt-tipped cannula to place horizontal threads of HA filler across the fold within the deep dermis and subdermal (superficial fat) layer. This strategy supports the skin internally, aiming for a natural correction with low product volume and reduced risk of vascular compromise.

The term "*Bridging*" refers to the creation of **bridge-like internal support structures** beneath the nasolabial fold using small, precisely placed filler threads. These threads act as scaffolding, helping to lift and soften the fold without overfilling or distorting the natural contours of the face.

This study will evaluate the clinical and subjective outcomes of this technique using AILEENE Vol. 2, a CE-marked and MHRA-registered HA filler.

2. Objectives

Primary Objective

To assess changes in nasolabial fold appearance using the validated Nasolabial Fold Severity Scale (NLFSS) from baseline to 6 months.

Secondary Objectives

- To assess patient satisfaction using the Global Aesthetic Improvement Scale (GAIS).
- To measure treatment longevity over a 6-month period.
- To document how many participants request a top-up treatment at 4 weeks.
- To evaluate subjective feedback using a short 5-item PROM (Patient-Reported Outcome Measure).

3. Study Design

This study is designed as a prospective, interventional, single-arm clinical evaluation. It will be carried out at a single private aesthetic clinic in the UK and aims to assess the performance, safety, and patient satisfaction associated with a specific dermal filler technique used in routine aesthetic practice.

A total of 60 adult participants will receive one treatment session with AILEENE Vol. 2 dermal filler using the Bridging Technique. Participants will attend a total of four clinic visits over a six-month period, with an additional check-in conducted remotely at two weeks post-treatment. An optional top-up may be offered at the four-week visit, depending on clinical judgement and patient preference.

This is an open-label study with no control group. The intention is to evaluate the technique in a real-world clinical setting, using standardised outcome tools and anonymised photographic assessments.

Key elements of the study design are as follows:

- **Study type:** Prospective, single-arm, non-randomised, interventional
- **Setting:** Ascencia Aesthetics Academy, Warrington (private non-NHS site)
- **Sample size:** 60 participants
- **Product:** AILEENE Vol. 2 dermal filler (maximum of 1.0ml per participant)
- **Injection method:** Bridging Technique using a 25G blunt-tipped cannula
- **Injection plane:** Deep dermis / subdermal (superficial fat layer)
- **Follow-up visits:** Day 0 (treatment), Week 2 (virtual check-in), Week 4, Month 3, and Month 6
- **Outcome assessments:** NLFSS scoring, GAIS, a 5-item patient-reported outcome questionnaire (PROM), and documentation of any adverse events

This design was chosen to provide observational performance data for a CE-marked, MHRA-registered product used in a novel but routine aesthetic application. The absence of a control arm reflects the exploratory nature of the study and the focus on documenting standard clinical outcomes in a well-defined patient group.

4. Eligibility Criteria

Inclusion Criteria

- Adults aged 30 to 65 years
- Bilateral nasolabial folds graded ≥ 2 on the NLFSS
- General good health
- Willingness to abstain from additional facial aesthetic procedures for the study duration
- Capacity to provide written informed consent
- Individuals of childbearing potential will be required to undergo a urine pregnancy test on the day of treatment. The test will be provided at the clinic. Only those with a negative result will be eligible to proceed with treatment on that day.

Exclusion Criteria

- Known allergy to hyaluronic acid, lidocaine, or any filler components
- Active local skin infection or inflammation
- History of permanent implants or semi-permanent fillers in the treatment area
- Anticoagulant therapy or bleeding disorder
- Pregnancy or breastfeeding:
 - There is currently insufficient research to establish the safety of dermal fillers, including AILEENE Vol. 2, during pregnancy or breastfeeding. Although no specific risks to the mother or fetus have been conclusively identified, the absence of evidence does not confirm the absence of risk. As a precaution, individuals who are pregnant, planning to become pregnant, or breastfeeding are not eligible to participate in this study and should not undergo this treatment.
- Keloid or hypertrophic scarring history
- Uncontrolled diabetes or severe systemic illness
- Recent cosmetic procedures in the lower face (within 6–12 months depending on treatment type)

5. Study Schedule

Each participant will be involved in the study for a period of six months and will attend four in-person visits, along with one virtual check-in. The schedule is as follows:

- **Visit 1 (Day 0):** Following informed consent and screening, participants will undergo baseline assessments, including clinical photographs, and will receive the initial treatment using the Bridging Technique.
- **Check-in (2 weeks post-treatment):** A virtual follow-up will be conducted by phone or video to assess short-term safety and patient experience.
- **Visit 2 (Week 4):** Participants will return for an in-clinic review. Standardised photographs will be taken, PROMs collected, and an optional top-up treatment offered if clinically indicated.
- **Visit 3 (Month 3):** A follow-up appointment will assess progress, capture updated photography, and gather further feedback using GAIS and PROMs.
- **Visit 4 (Month 6):** The final study visit will include repeat clinical photography, final PROM completion, and closure of participation.

6. Outcome Measures

Primary Endpoint

Change in NLFSS score from baseline to 6 months, assessed by blinded independent reviewers using anonymised photographs.

Statistical Method: Paired T-Test

Secondary Endpoints

- GAIS scores at each follow-up
- Subjective PROM results on satisfaction, comfort, and naturalness
- Proportion receiving top-up filler at Week 4
- Documentation of adverse events

7. Data Management

Each participant will be assigned a unique study ID.

Clinical photographs will be obtained using the Bitmoji A5-AI device, stripped of metadata and securely stored.

All data will be recorded electronically in **Clever Clinic**, with access restricted to the investigator and authorised staff. Data will be managed in accordance with the **UK GDPR** and **Data Protection Act 2018**.

8. Safety and Risk Considerations

Risks are consistent with routine aesthetic filler procedures and include bruising, swelling, tenderness, nodules, asymmetry, or in rare cases, vascular occlusion or allergic reaction.

Emergency protocols, including the use of hyaluronidase, will be in place. The Chief Investigator has extensive training in complication management. No data monitoring committee is required due to the low-risk profile and non-NHS setting.

9. Insurance and Indemnity

The study is sponsored by **JNL Aesthetics Limited**, which holds indemnity cover. The Chief Investigator holds additional professional indemnity insurance. This is not a CTIMP and does not involve the use of an investigational device.

10. Dissemination

Study findings will be submitted for publication in academic journals and presented at national or international conferences. A plain-language summary will be made available to participants who opt in to receive it. The study will be listed on **ClinicalTrials.gov** prior to the first enrolment.

End of Document

Protocol Version: 1.0 Date: 01 August 2025

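### The allergy exclusion omits hyaluronidase, the only emergency agent the protocol names, so a person with a known allergy to it remains eligible

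*Protocol*

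**What the plan says.** Three parts of the Protocol bear on this.

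- **Section 4, Exclusion Criteria.** The only criterion about allergy is "Known allergy to hyaluronic acid, lidocaine, or any filler components".
- **Section 8, Safety and Risk Considerations.** After the common local reactions, the risk list ends with "or in rare cases, vascular occlusion or allergic reaction". The next sentence reads "Emergency protocols, including the use of hyaluronidase, will be in place". This is the only place in the document where hyaluronidase appears, and no other emergency agent is named.
- **Section 5, Study Schedule.** Screening and the first injection belong to the same visit, Visit 1 (Day 0): "Following informed consent and screening, participants will undergo baseline assessments, including clinical photographs, and will receive the initial treatment".

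Section 1 describes the product as "a CE-marked and MHRA-registered HA filler". Nowhere is hyaluronidase described as one of its components.

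**The concern.** An allergy exclusion in an elective procedure should keep out people for whom the procedure, or the foreseeable treatment of its complications, carries an avoidable hazard. The criterion covers what every participant receives by design. It does not cover the agent that the safety section holds ready if something goes wrong.

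At stake is one unlucky combination: a participant with a known hyaluronidase allergy who then needs emergency treatment. The one agent the Protocol names might then be unsafe to give, and no alternative is stated. Because the treatment is cosmetic, declining such a person beforehand costs that person little. The Protocol already takes a precautionary line elsewhere, for example by excluding pregnancy and breastfeeding on the ground that safety is not established.

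The point concerns participant safety only and has no bearing on the statistical results. Sections 4 and 8 do not contradict each other; the criterion is simply drawn too narrowly.

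**Working it through.** The Protocol gives no figure to reproduce here. The check is a reading of the criteria against the safety section, followed by an illustration of size.

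**Step 1: count the criteria (Section 4).** There are 6 inclusion and 8 exclusion criteria, so 6 + 8 = 14. One of the 14 concerns allergy, and none of the 14 names hyaluronidase.

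**Step 2: could another criterion catch the allergy by its wording?**

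| Candidate | Does it reach a known hyaluronidase allergy? |
|---|---|
| The filler-components part of "Known allergy to hyaluronic acid, lidocaine, or any filler components" | No. Hyaluronidase is held for emergencies and is not described as part of the filler. |
| "General good health" | Not by its wording. A person with a drug allergy can be in good health. |
| "Uncontrolled diabetes or severe systemic illness" | No. A drug allergy in a well person is neither. |
| General investigator-discretion exclusion | None is listed. |

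**Step 3: when could it be caught?** Screening and injection share Visit 1, so that screening is the only stated point to ask before the first injection. The Week 2 check-in comes afterwards, and the optional Week 4 top-up may expose some participants a second time.

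**Step 4: illustrative size.** The Protocol gives no frequency for hyaluronidase allergy and calls occlusion only rare. Let *a* be the frequency of the allergy and *o* that of occlusion, each per participant. Both are assumptions, each taken over 0.1% to 1%, and the two are assumed independent. With n = 60 (Section 3), the chance of at least one participant having both is

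1 − (1 − a·o)^60.

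| a | o | a·o | Chance of at least one joint case in 60 |
|---|---|---|---|
| 0.001 | 0.001 | 0.000001 | 0.006% |
| 0.001 | 0.01 | 0.00001 | 0.06% |
| 0.01 | 0.001 | 0.00001 | 0.06% |
| 0.01 | 0.01 | 0.0001 | 0.60% |

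The table shows only the order of magnitude under those assumptions and is not an estimate for this trial.

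**The case against.** The case for leaving the criterion alone has four parts.

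- **Coherent scope.** The criterion lists what every participant is given. Hyaluronidase is a contingency that most or all will never receive, and on the same logic every agent in an emergency kit would need its own exclusion. This has some force as a general principle. But hyaluronidase is the only agent the Protocol itself chose to name, so covering it does not open an endless list.
- **Unseen emergency procedures.** Section 8 refers to emergency protocols that are not reproduced, and its word *including* signals that hyaluronidase is one element among others. That stands: alternatives may exist. None is stated, however, and such procedures take effect only once an elective injection has been given.
- **Clinical premise.** The Protocol does not say that hyaluronidase can cause allergy, or for which complication it is held. That is true. The argument needs only the plain point that a known allergy to an agent is a reason for caution in giving it, which requires no outside source. Whether to exclude such a person or to plan an alternative is a matter of judgement.
- **Practice already covers it.** Screening is not itemised, the Chief Investigator is trained in managing complications, and meeting the criteria does not oblige anyone to treat. All of this stands and lowers the risk in practice. It does not change who is eligible on paper.

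The event is also very unlikely, which is why the point is rated as low as it is. Eligibility is protocol content, so a statistical analysis plan would not be the place to settle it.

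**Conclusion.** The concern holds as a minor design point to consider. Followed literally, the eligibility rules admit a well person with a known allergy to the one emergency agent the Protocol names.

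The number of people affected cannot be derived from the document. Harm requires the allergy and a complication needing the agent in the same participant, and the illustrated chance is well below 1% even at the upper end of the assumed range. That range depends entirely on the assumed frequencies and on independence; the textual finding depends on neither.

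**What to change.** Insert hyaluronidase after lidocaine in the Section 4 allergy exclusion, and add a matching question to the Visit 1 screening, to be answered before injection.

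This takes one added word in one criterion and one screening question. The downside is that an otherwise eligible person will occasionally be turned away; the effect on recruiting 60 participants should be negligible.

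### No safety record is scheduled between the Day 0 injection and the two-week remote check-in, so injection reactions that resolve early depend on recall or spontaneous report and may be under-counted

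*Protocol*

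**What the plan says.** Section 3 states that the study "aims to assess the performance, safety, and patient satisfaction associated with a specific dermal filler technique". It lists the contacts as "Day 0 (treatment), Week 2 (virtual check-in), Week 4, Month 3, and Month 6". Among the outcome assessments it names "a 5-item patient-reported outcome questionnaire (PROM), and documentation of any adverse events", without tying adverse events to a visit or a method.

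For Visit 1, Section 5 says that after consent and screening "participants will undergo baseline assessments, including clinical photographs, and will receive the initial treatment using the Bridging Technique". Nothing is listed after the injection. The next contact is the two-week check-in: "A virtual follow-up will be conducted by phone or video to assess short-term safety and patient experience". It is the only contact in Section 5 with a named safety purpose. The optional top-up falls at Week 4, and the next scheduled contact after it is Month 3.

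Section 6 has "Documentation of adverse events" as a secondary endpoint, with no collection method or time window. Section 8 says that the risks "include bruising, swelling, tenderness, nodules, asymmetry, or in rare cases, vascular occlusion or allergic reaction". It gives no frequency or duration for any of them.

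**The concern.** Bruising, swelling and tenderness come first in the Section 8 list, and they follow the injection itself. If such a reaction appears and clears within two weeks, nobody is scheduled to see it, and the participant has no form on which to note it. A phone or video call at Day 14 cannot examine something that has gone. It can only ask what the participant remembers.

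Forgetting or playing down a mild, resolved reaction lowers the count and the recorded grade, so the likely direction of error favours the technique. The study has no control arm, so no comparator shares the incomplete capture and offsets it: the observed reaction rate is the whole safety result. Nor can an analysis plan repair this later, because it cannot recover observations that were never recorded.

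**Working it through.** The protocol states no figure for reaction rates, durations or capture, so there is nothing to reproduce. The check is a reading of the schedule, followed by an illustration on assumed values.

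**Step 1: what is scheduled (Sections 3 and 5).**

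| Contact | Safety content named in Section 5 |
|---|---|
| Day 0, in clinic | none after the injection |
| Day 1 to Day 13 | no contact, no diary or checklist |
| Week 2, remote | short-term safety |
| Week 4, in clinic, optional top-up | none named |
| Month 3, in clinic | none named |
| Month 6, in clinic | none named |

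**Step 2: length of the gaps.** From injection to the first scheduled safety contact: 14 days. From a Week 4 top-up to Month 3: 3 × 30.44 − 28 = 63.3 days, about nine weeks.

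**Step 3: routes into the record.** A reaction still present at Week 2 can be reported as current. A reaction that has resolved by then can enter only if it was noticed in clinic on Day 0, reported unprompted, or recalled at the check-in. None of these is a prompted record made at the time.

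**Step 4: scale, on assumed values only.** Let p be the true proportion of participants with an early reaction and c the share of them captured. Expected recorded cases = 60 × p × c, and the reported rate = p × c. N = 60 is from Section 3; p and c are assumptions.

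| True rate p | True cases | c = 60% | c = 80% | c = 95% | c = 100% |
|---|---|---|---|---|---|
| 20% | 12.0 | 7.2 | 9.6 | 11.4 | 12.0 |
| 40% | 24.0 | 14.4 | 19.2 | 22.8 | 24.0 |
| 60% | 36.0 | 21.6 | 28.8 | 34.2 | 36.0 |

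At p = 40% the reported rate runs from 0.40 × 0.60 = 24% to 40%. The shortfall equals 1 − c, so it runs from none to 40% of cases and is set wholly by the assumed c. Neither the documents nor data collected on this schedule would show where in that range the study lies.

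**The case against.** The strongest reply is that the schedule leaves less uncovered than it seems to. Section 3 commits to documenting any adverse event and ties this to no visit, so a reaction seen in clinic on Day 0 or phoned in later falls within it. Section 5 is also not exhaustive: it names GAIS only at Month 3, although Section 6 sets it at every follow-up. Silence in the Visit 1 entry is therefore weak evidence that nothing will be noted that day. This stands, and it is why one cannot say that all early reactions are recorded from memory. It does not close the gap, because that commitment has no time, prompt or method for Day 0 to Day 14.

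A reader might go further and infer that early reactions will be under-counted, or that they dominate the endpoint. The documents support neither. Section 8 gives no rates, does not call the reactions short-lived, and lists nodules and asymmetry beside bruising and swelling.

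A reader might also put a number on the bias from assumed durations. With exponential durations of median m days, the share still present at Day 14 is 2^(−14/m): 3.9%, 14.4%, 25.0% and 37.9% for m = 3, 5, 7 and 10. The complement, 62% to 96%, is the share that has resolved by Day 14 under those assumptions, not the share missed. A resolved reaction that is reported at Week 2 is counted, and with complete recall the loss is zero for every m.

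Finally, the protocol promises no estimate of onset or duration, calls the study exploratory and sets no safety threshold. That is fair. It lowers the priority of the point but does not remove it, since safety is still a stated aim with its own endpoint.

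**Conclusion.** The point holds as a limited weakness of the schedule. No safety assessment is scheduled, and no record made at the time is described, between the injection and the two-week remote contact. Bruising, swelling or tenderness that resolves before then depends on recall or spontaneous report. Incidence and worst grade may be understated, probably in the technique's favour. That direction is a judgement about how people report mild, resolved reactions, not something the documents show.

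The size is unknown. The illustration gives a loss of anywhere from none to 40% of cases, and it rests entirely on an assumed capture share. The same weakness applies after a Week 4 top-up, with a longer interval to the next scheduled contact. The primary NLFSS comparison is unaffected. This is a cheap improvement of lower priority.

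**What to change.** In Section 5:

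- Add one record of injection-site findings on Day 0, made after treatment.
- Give each participant a short checklist of the Section 8 reactions, graded none, mild, moderate or severe, for Day 0 to Day 14, and collect it at the Week 2 check-in.
- Use the same form after any Week 4 top-up, returned by message or at the next contact.

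In Section 6, state that incidence and worst grade for the adverse-event endpoint are reported from this form, alongside any other adverse event documented.

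The cost is a one-page or online form and a few protocol sentences. Each participant gives about a minute a day: 15 daily entries, or 15 × 60 = 900 in all before any top-ups. Some entries will be missing or filled in afterwards, which brings part of the recall problem back, so completion should be reported. The reported reaction rate will probably be higher. The change concerns data capture only and alters no treatment or care rule.

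### Does the single-arm design leave the photograph reviewers unmasked to before and after, and so the primary endpoint open to expectation bias?

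*Protocol*

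**What the plan says.** Section 3 describes the study type as "Prospective, single-arm, non-randomised, interventional" and adds: "This is an open-label study with no control group". On size it states: "A total of 60 adult participants will receive one treatment session".

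Section 6 defines the primary endpoint as "Change in NLFSS score from baseline to 6 months", "assessed by blinded independent reviewers using anonymised photographs", and names a paired t-test. Section 5 places the baseline photographs at Day 0, where "participants will undergo baseline assessments, including clinical photographs, and will receive the initial treatment"; photographs are taken again at Week 4, Month 3 and Month 6.

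Section 7 covers handling. "Each participant will be assigned a unique study ID", and the photographs are "stripped of metadata and securely stored".

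The protocol does not say what the reviewers are blinded to, how image files are coded, in what order they are shown, or whether they are scored singly or side by side.

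**The concern.** In a randomised trial, a blinded assessor is ordinarily one who does not know the treatment arm. Here everyone has the same treatment, so that meaning is not available. The masking that protects a before/after score is masking to visit, and the protocol does not spell it out. The measures it does describe (anonymised images, participant IDs, stripped metadata) look aimed mainly at confidentiality. A set of images could meet all of those measures and still reach the reviewers as a Day 0 and Month 6 pair.

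A reviewer who knows which image is the later one may expect a milder fold and score it so. With no control group, that expectation does not cancel. It enters the mean change in full and cannot be separated from a treatment effect. The paired t-test compares the mean change with zero, so a modest systematic shift could produce a positive primary result. Knowledge of the visit during scoring cannot be undone afterwards.

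**Working it through.** **Step 1: how much a rater shift would matter if reviewers knew the visit.**

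Input from the protocol: n = 60 (section 3), with a paired t-test on the change (section 6). The protocol gives no significance level, SD of change or likely rater shift, so there is no figure of its own to reproduce. Assumed for illustration: two-sided 5% level, SD of change 0.5 to 1.0 grade, systematic shift b of 0.1 to 0.3 grade, true change zero, complete data.

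Smallest observed mean change that reaches significance: t(0.975, 59) / √60 = 2.001 / 7.746 = 0.258 SD. That is 0.258 × 0.5 = 0.13 grade at SD 0.5 and 0.26 grade at SD 1.0.

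Probability of a significant result from the shift alone: noncentral t with 59 degrees of freedom and noncentrality b√60 / SD. For b = 0.2 and SD = 0.7 the noncentrality is 0.2 × 7.746 / 0.7 = 2.21, which gives 0.586.

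| SD of change | b = 0.1 | b = 0.2 | b = 0.3 |
|---|---|---|---|
| 0.5 | 33% | 86% | 99.5% |
| 0.7 | 19% | 59% | 90% |
| 0.9 | 14% | 40% | 72% |
| 1.0 | 12% | 33% | 63% |

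The nominal rate is 5%. The table describes any constant bias in any one-sample test at n = 60. It takes the bias as given.

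**Step 2: whether the protocol lets that bias in.**

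- Section 6 attaches three separate properties to the assessment: the reviewers are blinded, they are independent, and the photographs are anonymised. Anonymisation is not the only safeguard, and *blinded* has to mean something beyond it.
- With one treated group (section 3), blinding to arm is impossible. For a change between two visits, what is left to mask that matters is the visit. Top-up status could also be masked, but that is secondary here. The premise of the concern therefore points to blinding to visit as the ordinary reading.
- Removing metadata (section 7) would take out an embedded capture date. It does not control file names or display order, but it is a step towards hiding the visit as well as identity.
- The study ID in section 7 is assigned to the participant. The protocol does not say that reviewers see images under that ID, in labelled pairs, or in visit order. On presentation it is silent.

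If reviewers are in fact blinded, as section 6 requires, b has no route into the score through knowledge of the visit, and the table does not apply.

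**Step 3: whether related additions would correct anything.**

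Defining baseline as the reviewers' score of the Day 0 photograph, rather than the eligibility grade in section 4, adds nothing: section 6 already has the reviewers assess the change from baseline, and Day 0 photographs exist for that purpose. Repeat reads of a subset would describe rater agreement but would not alter the primary result. Pooling all four photographed visits would mean 60 × 4 = 240 image sets, against 60 × 2 = 120 for the primary endpoint, so it is not free of work.

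**The case for a change.** The strongest case for a change is that what assessors are blinded to is a design feature and belongs in the protocol. The word has no standard meaning in a single-arm study, and a team could remove identity, show labelled before/after pairs, and still claim to have followed the text. The cost of preventing this is small: neutral file codes, a random order and single-image scoring, all before any reading starts.

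Part of this stands. The protocol does not name the object of the blinding, and neither anonymisation nor metadata removal guarantees that the visit is hidden. A sentence saying so would be clearer. But reviewers shown labelled before/after pairs would not be blinded in any sense relevant to this endpoint, so that team would be departing from section 6 rather than following it. Coding, ordering and single versus paired reading are details commonly left to reading instructions or an analysis plan, and neither is at hand.

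**Conclusion.** No change to the plan follows. The protocol states the safeguard and leaves its mechanics unwritten, a gap that a team carrying out a blinded photographic read fills sensibly by hiding the visit. The illustrative false-positive rates (59% for a 0.2-grade shift at SD 0.7, and 33% to 86% for the same shift across SDs of 1.0 down to 0.5) are correct as arithmetic. They rest on an assumed SD, an assumed shift and reviewers who know the visit, and the protocol supplies none of the three.

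This conclusion assumes that *blinded* in section 6 is carried out as blinding to visit. If the images were in fact read as labelled pairs, the bias would be real and its possible size would be that shown in the table. Masking to visit would not in any case remove other single-arm biases such as regression to the mean.
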